#### *Consent*

Consent will be sought prospectively from living individuals accrued into the study from January 2006 to access medical records and tumour blocks.

This study has been active since 1992 and all blood samples have informed consent for PrCa predisposition gene studies. Outside tumour blocks and pathological samples have informed consent for molecular studies. Many of The Royal Marsden NHS Foundation Trust PrCa tumour

samples also have consent under a clause in the operation consent form in use at that time that 'material removed may be used for research purposes'. Some tissue was collected from local hospitals under the auspices of the previous protocol and the consent form did not explicitly state separate consent for the use of tissue at that time, although it was part of the approved protocol. Many patients are now deceased. It is therefore proposed that tissue and medical record data collected retrospectively will be analysed anonymously with no results fed back to patients as this would not impact upon their care. An exception is results from the studies on blood where findings in PrCa predisposition genes could have implications for relatives.

Those patients who are still living who have previously taken part in the study from 1992 until the present and who have not taken part in the environmental questionnaire part of the study will be invited to take part in this part of the study. New consent will be obtained for this.

#### **4.2 The Study at Collaborative Centres throughout the UK. Many of these are via the NCRN network.**

This is conducted as for the Study at The Royal Marsden except, the only groups of patients eligible for this part of the study are (a) men with PrCa presenting at a young age ( $\leq 60$  years)\* refer to page 14 or (b) PrCa in first, second or third-degree related pairs where one is  $\leq 65$  years at diagnosis or (c) a total of 3 or more relatives with PrCa at any age on the same side of the family

The two parts (4.1) and (4.2) are now called the UKGPCS (UK Genetic Prostate Cancer Study).

##### *Proposed analyses on the samples*

The samples will be used to find PrCa predisposition genes using molecular analyses. These investigations are solely for research to find a PrCa predisposing gene(s) and no results would be conveyed to the patients until such a gene(s) had been found. If such a gene(s) is found, then no patient will have genetic testing for abnormalities in such a gene without prior genetic counselling and this would be on a newly taken blood sample. Only those patients who wish (as stated on their consent form) to be informed of research findings will be contacted. If this occurs more than 6 months after the last contact with the patient, then contact would be via the GP.

Data will be correlated with medical records and treatment outcome to find genetic alterations that are associated with prostate cancer development and/or prognosis.

[figure not shown]
Tumour material will be collected and stored at  $-70^{\circ}\text{C}$  in freezer space currently available at The Institute of Cancer Research. Tumour will also be stored in RNA later. Paraffin embedded tumour will be made into tissue microarrays and sections cut. This will be used for molecular biology analysis. Specimens for biomarkers will be taken from untreated patients and processed in a manner suitable for future proteomic and metabolomic assays.

Cases and their relatives may be flagged by the cancer registry to confirm a diagnosis of prostate cancer, a date of death and cause of death. This will be done via the Data linkage Service (formerly known as Medical Research Information Service), using records maintained by The NHS Information Centre and the Health & Social Care Information Centre.

Clinical details are collected routinely as part of the medical care and clinical follow up record on patients with prostate cancer and these include disease parameters (e.g. stage, grade) and treatment outcome (e.g. survival data, side effects of treatment). We will also request follow-up data, approximately 2, 5 and 10 years after the patient has consented, to record any relapse, treatment and survival data that have occurred since diagnosis. We will link the genetic findings with these clinical data to try to identify genetic markers of disease parameters (e.g. those which predict for poorer prognosis or worse late toxicity from treatments such as radiotherapy). These data would be analysed anonymously after linking the clinical and genetic datasets. No overall results would be feedback to participants. We will supply anonymised data from this to other studies under an MTA (e.g the Genepi study). This would only be to a central database managed under the auspices of GCP and would only be anonymised data. No individual would be identifiable to the holders of such a database.

### 4.3 Flowchart of UKGPCS

#### WHAT THE RECRUITING CENTRES NEED TO DO

## **5 STUDY TYPE - THERAPEUTIC REGIMENS, EXPECTED TOXICITY, DOSE MODIFICATIONS**

None – this is an observational study.

## **6 POTENTIAL ADVERSE EVENTS**

Occasionally patients may be concerned about their family history and if so, we have clinically trained cancer genetic counsellors who can support them and refer them to appropriate clinical cancer genetics specialists via their GP. We also have access to psychological support counseling if an individual is distressed.

## **7 STATISTICAL CONSIDERATIONS**

For large scale empirical association studies, stringent thresholds of statistical significance are required in order to avoid false positive claims of association – a threshold of  $P < 0.0000001$  has been suggested. Large sample sizes are required to obtain this level of statistical significance for common susceptibility alleles that are likely to confer quite moderate risks of disease.

At this level of significance, 10,000 cases and 10,000 controls will provide approximately 75% power to detect an allele with a population frequency of 1% that confers a 2 fold increase risk of prostate cancer, or an allele with a frequency 5% that confers a 1.3 fold risk. These alleles would explain approximately 1% of the observed familial risk of prostate cancer, and hence are of plausible magnitude. This is therefore the target size of the systematic series.

Cases with a positive family history of prostate cancer provide greater power to detect associations since the frequency of susceptibility alleles will be higher in this group. Cases with early onset prostate cancer are also potentially more powerful since the familial risk of prostate cancer is greater at young ages. We aim to collect at least 10,000 cases of PrCa diagnosed at  $\leq 60$  years together with cases from 2,000 affected families.

Taken together, the total cases will be equivalent to approximately 26,000 cases, depending on how many cases we recruit from each affected family (we have allowed for an average of 3 cases per family to equal 6,000 familial cases). They would therefore have 75% power to detect an allele with frequency of 1% that confers a 1.5 fold increased risk of PrCa or an allele with a 5% frequency that confers a 1.2 fold risk.

Association studies will utilise these latter groups in the initial stages of analysis while using the systematic series to provide confirmation of associations and a direct estimate of the relative risk associated with any susceptibility allele. Collection of familial and early onset cases will therefore remain a priority in the study. Total numbers of PrCa cases therefore sought are:

10,000 from the Royal Marsden (The Systematic Series); 10,000 early onset cases (outside referrals with PrCa aged  $\leq 60$  years at diagnosis); approximately 6,000 cases from 2,000 families (from outside referrals).

Statistical analyses using clinical data from the Royal Marsden Foundation Trust will be specified and documented in the form of Statistical Analysis Plans in accordance with the Royal Marsden Standard Operating Procedures. These Statistical Analysis Plans will be submitted to the Royal Marsden Committee for Clinical Research (CCR) for review and approval.

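### The power given for the 1% allele with a 2-fold risk is about 99.7%, not about 75%; the paired 5%, 1.3-fold figure is right and still supports the 10,000 target

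*Protocol*

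**What the plan says.** Protocol section 7 (Statistical Considerations) takes its significance level from the remark that "a threshold of $P < 0.0000001$ has been suggested". For equal groups of 10,000 tested at that level, it claims "approximately 75% power to detect an allele with a population frequency of 1% that confers a 2 fold increase risk of prostate cancer". A second benchmark is put forward as reaching the same power with the same numbers: "or an allele with a frequency 5% that confers a 1.3 fold risk". The section adds that alleles of this kind would account for roughly 1% of the familial risk and so are plausible, and concludes: "This is therefore the target size of the systematic series".

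The section gives the sample size, significance level, allele frequencies, risks and power. It does not give the genetic model, the test or the sidedness.

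**The concern.** The sentence presents the two alleles as interchangeable: same sample size, same significance level, same power. A doubling of risk at 1% frequency is a much stronger signal than a 30% increase at 5%, so it was worth checking whether one calculation yields 75% for both.

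This is the sentence from which the size of the systematic series is drawn. Section 1.1 says the number of samples was increased to gain power for rare variants, so the 1% figure is the one closest to that purpose. If it is wrong, readers are misinformed about what the series can detect or confirm among low-frequency alleles.

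**Working it through.** **Inputs, all from Protocol section 7:** "10,000 cases and 10,000 controls"; P < 1e-7; (q, RR) = (0.01, 2) and (0.05, 1.3); stated power about 75% for each.

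**Assumptions, not in the protocol:** two-sided test; per-allele model, so 20,000 case alleles against 20,000 control alleles; control allele frequency equal to the population frequency q. The dominant model was also run.

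**Formulas**

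- Case allele frequency: p1 = q·RR / (q·RR + 1 − q), with p0 = q
- Null standard error: SE0 = √[2·p̄(1 − p̄)/20,000], where p̄ = (p0 + p1)/2
- Alternative standard error: SE1 = √[(p1(1 − p1) + p0(1 − p0))/20,000]
- Power = Φ[(p1 − p0 − z·SE0)/SE1], where z = 5.327 for two-sided 1e-7

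**Step 1: the figure that reproduces (5%, 1.3-fold)**

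- p1 = 0.065/1.015 = 0.06404; difference 0.01404
- SE0 = 0.002319 and SE1 = 0.002318
- (0.01404 − 5.327 × 0.002319)/0.002318 ≈ 0.73, so power = 76.7%
- 75% power needs about 9,820 cases and 9,820 controls.

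**Step 2: the figure that does not (1%, 2-fold)**

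- p1 = 0.02/1.01 = 0.01980; difference 0.00980
- SE0 = 0.001212 and SE1 = 0.001211
- (0.00980 − 5.327 × 0.001212)/0.001211 ≈ 2.77, so power = 99.7%
- 75% power needs about 5,500 per group. With 10,000 per group, 75% power corresponds to a risk of about 1.70 (1.71 dominant).

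**Step 3: do the unstated choices matter?** Power at 10,000 + 10,000 and 1e-7, two-sided unless noted:

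| Reading | 1%, 2-fold | 5%, 1.3-fold |
|---|---|---|
| Per-allele | 99.7% | 76.7% |
| Per-allele, one-sided | 99.8% | 80.4% |
| Per-allele, continuity-corrected | 99.7% | 76.0% |
| Log odds ratio Wald test | 99.6% | 76.2% |
| Dominant (carriers, Hardy-Weinberg) | 99.6% | 67.8% |
| Frequency read as carrier frequency | 65.3% | 14.8% |
| As above, one-sided, case frequency = RR × q | 73.2% | 26.0% |
| Stated risk read as the homozygote risk | 5.7% | 0.9% |
| Recessive | about 0% | about 0% |

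Simulation (200,000 runs) gives 99.8% per-allele and 99.7% dominant for the 1% allele, and 76.7% and 68.0% for the 5% allele. Tightening the per-allele significance level to 1e-10 still leaves 94.8% for the 1% allele, while the 5% allele falls to 34.0%. No row gives about 75% in both columns.

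**Step 4: effect on the familial-risk sentence.** Under a multiplicative model, the sibling risk ratio due to one allele is λ = [1 + q(1 − q)(RR − 1)² / (2(q·RR + 1 − q)²)]². Its share of familial risk is ln λ / ln 2.2, taking the first-degree relative risk of 2.2 from Protocol section 1.

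- 1%, 2-fold: λ = 1.00973, share about 1.2%
- 1%, 1.7-fold: λ = 1.00479, share about 0.6%
- 5%, 1.3-fold: λ = 1.00415, share about 0.5%

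**The case against.** **A different reading might rescue the figure.** Taking 1% as a carrier frequency brings the power down to between 65% and 73%, close to the text at its upper end. But the protocol speaks of an allele with a population frequency, and the same reading drops the companion to between 15% and 26%. One could also suppose that the 1% allele is genotyped only through an imperfect marker: a squared correlation of about 0.55 (5,500/10,000) would give 75%. The protocol mentions no such allowance, and the 5% figure would have to be exempt from it, since 76.7% is already its power with perfect genotyping. Neither reading stands.

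**The consequences are small.** This part stands. The two alleles are alternatives, and the 5%, 1.3-fold one justifies about 10,000 per group without help from the other. The mistake is conservative, the figures are offered as approximate, and no test, threshold or recruitment rule depends on the 1% figure.

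**A reader might infer that the target is nearly twice what is needed**, because 5,500 per group is enough for the 1%, 2-fold allele. The protocol does not support that. At 5,500 per group (11,000 alleles), both standard errors in step 1 grow by √(10,000/5,500) = 1.348, and power for the 5%, 1.3-fold allele falls to about 20%.

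**A reader might also infer that the gain from expanding to 26,000 cases is overstated**, because it appears to run from 2-fold to 1.5-fold. That cannot be settled: section 7 gives no number of controls for that analysis. At 1% frequency, 75% power corresponds to about 1.59-fold with 10,000 controls and about 1.41-fold with 26,000, so the protocol's 1.5-fold lies inside the range.

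**Conclusion.** The stated power for the 1%, 2-fold allele is wrong by about 25 percentage points: about 75% in the text, 99.7% per-allele or 99.6% dominant by calculation. The companion figure is right on the per-allele model (76.7%), so the sentence is mistaken in treating the two alleles as equally detectable.

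The result assumes a per-allele or dominant model, perfect genotyping and a standard two-group comparison. Sidedness and the choice of test hardly move it.

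Power is understated, so the study is not underpowered for this allele. The 10,000 target is unaffected: the 5%, 1.3-fold allele alone requires about 9,820 per group per-allele, or about 10,750 on a dominant model. This is an isolated, conservative numerical error in the sample-size rationale. It should be corrected because it misdescribes what the series can do for low-frequency alleles.

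**What to change.** Restate the sentence in section 7 so that 10,000 cases and 10,000 controls give more than 99% power for the 1%, 2-fold allele and about 75% for the 5%, 1.3-fold allele. Optionally add that 75% power at 1% corresponds to a risk of about 1.7-fold. Naming the model and sidedness (per-allele, two-sided) in the same sentence would let readers reproduce both figures.

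This is preferable to replacing 2-fold by 1.7-fold. That change would halve the 1% allele's share of familial risk, from about 1.2% to about 0.6%, so the next sentence, which puts the share at about 1%, would also need revision.

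The cost is one sentence. Recruitment targets, design and analysis do not change.

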## **8 INVESTIGATOR AUTHORISATION PROCEDURE**

Investigators will be authorised to register subjects in this trial only when they have returned to the Study Centre:

- A commitment statement / study acknowledgement form, indicating that they will fully comply with the protocol, to include an estimate of their yearly accrual and if any conflict of interest may arrive due to their participation in the trial,
- A copy of the letter of acceptance of the protocol by their local or national (whichever is applicable) ethics committee,
- A signed conflict of interest disclosure form: this document will be required only if a possible conflict is declared by the commitment form.

**ALL FORMS MUST BE DATED AND SIGNED BY THE RESPONSIBLE INVESTIGATOR OR ONE OF HIS/HER AUTHORISED STAFF MEMBERS.**

## **10 QUALITY ASSURANCE**

### **10.1 Control of data consistency**

Data forms will be entered in the database of the Study Data Centre at The Institute of Cancer Research and manual consistency checks will be performed on newly entered forms; queries will be issued in case of inconsistencies. Consistent forms will be validated by the Data Manager to be entered on the master database. Inconsistent forms will be kept "on-hold" until resolution of the inconsistencies has occurred.

## **11 ETHICAL CONSIDERATIONS**

### **11.1 Subject protection**

The responsible investigator will ensure that this study is conducted in agreement with either the Declaration of Helsinki (Appendix A) or the laws and regulations of the country, whichever provides the greatest protection of the subject.

The protocol has been written, and the study will be conducted according to the ICH Harmonised Tripartite Guideline for Good Clinical Practice (ref: <http://www.ifpma.org/pdfifpma/e6.pdf>).

The protocol will be approved by the MREC National Ethics Committee.

## **11.2 Informed consent and feedback of results**

Consent will be sought prospectively from living individuals accrued into the study from January 2006 to access medical records and tumour blocks in addition to consent for blood, saliva, urine and other tissue samples.

This study has been active since 1992 and all blood samples have informed consent for PrCa predisposition gene studies. Outside tumour blocks and pathological samples have informed consent for molecular studies. Many of The Royal Marsden NHS Foundation Trust PrCa tumour samples also have consent under a clause in the operation consent form in use at that time that 'material removed may be used for research purposes'. Some tissue was collected from local hospitals under the auspices of the previous protocol and the consent form did not explicitly state separate consent for the use of tissue at that time. Many patients are now deceased. It is therefore proposed that tissue and medical record data collected retrospectively will be analysed anonymously with no results fed back to patients as this would not impact upon their care. An exception is results from the studies on blood where findings in PrCa predisposition genes could have implications for relatives; in these cases informed consent has been obtained from all samples being worked on in the study to date. We may request tissue samples from other members of the family where findings in PrCa predisposition genes need to be verified by further analysis of the family, or where unaffected relatives have expressed interest in taking part in the study. In the case of deceased relatives we would ask for written permission from the family to request tissue from the hospital where this was stored. In the case of a living relative we would ask this individual for written consent to obtain blood or other tissue samples to help with our research.

Those patients who are still living who have previously taken part in the study from 1992 until the present and who have not taken part in the environmental questionnaire part of the study will be invited to take part in this part of the study.

It will be emphasised that the participation is voluntary and that the subject is allowed to refuse further participation in the protocol whenever he wants. This will not prejudice the subject's subsequent care.

For European Community member states, the informed consent procedure must conform to the ICH guidelines on Good Clinical Practice. This implies that "the written informed consent form should be signed and personally dated by the subject or by the subject's legally acceptable representative".

## **12 ADMINISTRATIVE RESPONSIBILITIES**

### **12.1 The Study Team**

The PI, the Statistician, Study Co-ordinator and Laboratory Team Leader or their designated teams will be responsible for writing the protocol, reviewing and entering all case report forms/medical record (including the histology reports), performing molecular and statistical analyses and for writing the draft of the study results. The PI will also generally be responsible for answering all clinical questions concerning eligibility and the evaluation of the subjects.

#### ***Study Office***

The Study Office will be responsible for reviewing the protocol, collecting clinical data proformas controlling the quality of the reported data, and generating reports and analyses in cooperation with the Study Coordinator. All methodological questions should be addressed to the Study Office.

The UKGPCS Team, The Institute of Cancer Research, [name]  
[contact], [contact], E-mail : [[contact]](mailto:[contact])

**[contact] Mark FOR UKGPCS - [name]**

The Safety Desk will forward all SAE reports within 24 hours of receipt to the PI

## **13 TRIAL SPONSORSHIP AND FINANCING**

The study is financed by

- Cancer Research UK (Programme Grants to [name])
- NIH
- NIHR
- Prostate Cancer UK
- [name] Fund
- The Institute of Cancer Research (Everyman Campaign)
- Movember

The study is sponsored by The Institute of Cancer Research

## **14 PUBLICATION POLICY**

The Principal Investigator (PI), Co-PI and the Study Team, on the basis of the final analysis performed at the Data Centre will write the final publication of the study results.

Authors of the manuscript will include at least the PI, Statistician all collaborators who have entered at least 1 study individual (until 2006, known as the CR-UK/BPG/BAUS Section of Oncology Study Collaborators). All manuscripts will include an appropriate acknowledgement section, mentioning the supporting bodies.

The PI and The Statistician must approve all publications, abstracts and presentations based on subjects included in this study.

## 15 APPENDIX A

### World Medical Association Declaration of Helsinki Ethical Principles for Medical Research Involving Human Subjects

Adopted by the 18th World Medical Assembly

Helsinki, Finland, June 1964

and amended by the

29th World Medical Assembly, Tokyo, Japan, October 1975

35th World Medical Assembly, Venice, Italy, October 1983

41st World Medical Assembly, Hong Kong, September 1989

48th General Assembly, Somerset West, Republic of South Africa, October 1996

and the

52nd WMA General Assembly, Edinburgh, Scotland, October 2000

#### A. INTRODUCTION

1. The World Medical Association has developed the Declaration of Helsinki as a statement of ethical principles to provide guidance to physicians and other participants in medical research involving human subjects. Medical research involving human subjects includes research on identifiable human material or identifiable data.
2. It is the duty of the physician to promote and safeguard the health of the people. The physician's knowledge and conscience are dedicated to the fulfilment of this duty.
3. The Declaration of Geneva of the World Medical Association binds the physician with the words, "The health of my patient will be my first consideration," and the International Code of Medical Ethics declares that, "A physician shall act only in the patient's interest when providing medical care which might have the effect of weakening the physical and mental condition of the patient."
4. Medical progress is based on research which ultimately must rest in part on experimentation involving human subjects.
5. In medical research on human subjects, considerations related to the well-being of the human subject should take precedence over the interests of science and society.
6. The primary purpose of medical research involving human subjects is to improve prophylactic, diagnostic and therapeutic procedures and the understanding of the aetiology and pathogenesis of disease. Even the best proven prophylactic, diagnostic, and therapeutic methods must continuously be challenged through research for their effectiveness, efficiency, accessibility and quality.
7. In current medical practice and in medical research, most prophylactic, diagnostic and therapeutic procedures involve risks and burdens.
8. Medical research is subject to ethical standards that promote respect for all human beings and protect their health and rights. Some research populations are vulnerable and need special protection. The particular needs of the economically and medically disadvantaged must be recognized. Special attention is also required for those who cannot give or refuse consent for themselves, for those who may be subject to giving consent under duress, for those who will not benefit personally from the research and for those for whom the research is combined with care.
9. Research Investigators should be aware of the ethical, legal and regulatory requirements for research on human subjects in their own countries as well as applicable international requirements. No national ethical, legal or regulatory requirement should be allowed to reduce or eliminate any of the protections for human subjects set forth in this Declaration.

